5.2. Efficacy Endpoints

When plasmapheresis is scheduled during one of the clinical protocol monthly study visits, a sample of the plasma collected during plasmapheresis will be collected. Samples will be stored at $\leq -20^{\circ}\text{C}$ until tested and will be tested throughout the study shortly after collection. Tetanus antibody responses will be measured at a central laboratory using an enzyme-linked immunosorbent assay (ELISA) [VaccZyme Tetanus Toxoid IgG – Binding Site] and expressed as international units per mL (IU/mL).

5.3. Baseline and Other Assessments

A complete medical history and demography (gender, age, race, and ethnicity) will be collected at the screening visit. Medications being taken by the subject in the 7-day period prior to the first vaccination through the completion of the study along with complete immunization history will be recorded and reported on an eCRF.

Vitals signs, full physical examinations and hematocrit and total protein determinations as part of the routine plasmapheresis will be assessed during pre-donation screening.

Infectious disease testing will be performed on all plasma samples collected from plasma donations and if a subject is positive for any of these infectious diseases, they will be taken off study. In addition, RPR (syphilis test) is performed every 4 months. If the subject is a first time donor, they must have two sequential plasma donations that are negative for the following infectious diseases to be eligible for plasmapheresis: Anti-HIV-1/2, HBsAg, Anti-HCV, SPE/RPR, Indirect Coombs, and PCR testing for HIV-1, HBV and HCV, HAV, and Parvovirus B19.

An eligibility checklist will be completed at screening. If the subject is not eligible for the study, a Reasons Not Eligible eCRF will be completed.

A dipstick urinalysis will be performed that tests for protein, blood, leukocyte esterase, nitrates, pH, specific gravity, ketones, bilirubin, and glucose. A blood sample will also be collected for a serum creatinine test. These tests will be performed to monitor for the possible development of immune complex-mediated glomerular disease.

Anti-diphtheria antibody levels will be measured at a central laboratory using the EUROIMMUN Anti-Diphtheria Toxoid ELISA (IgG). High anti-diphtheria titers will be assessed for an association with an increase in reactogenicity.

6. Hypotheses to be Tested

Hypothesis tests will be performed in order to determine if there is an association between reactogenicity and anti-diphtheria titers. Null Hypothesis of no association between reactogenicity and anti-diphtheria titers will be tested on Slope obtained using simple linear regression analysis at alpha=0.01 using two-sided tests.

7. Sample Size

One hundred subjects will be enrolled in this study.

8. Data Quality Assurance

Data quality is maintained by ensuring accuracy of data, reviewing protocol prior to study start, auditing data according to GCP and periodic site monitoring by sponsor's designees. Written instructions will be provided for collection, preparation, and shipment of blood spot samples.

The Sponsor's designees will review source documents for accuracy and completeness during on-site and remote monitoring visits and any discrepancies will be resolved with the PI, as appropriate.

Significant and/or repeated noncompliance will be investigated and remedial action instituted when appropriate. Failure to comply with remedial actions may result in study site termination and regulatory authority notification.

9. Statistical Considerations

9.1. General Considerations

Descriptive statistics will be used to present study data. Continuous variables will be presented as number of observations (n), mean, standard deviation (SD), median, minimum (min) and maximum (max) values. Categorical and dichotomous variables will be presented as counts and percentages. As it is expected that titers will not be normally distributed, geometric means (GeoMean) will be used to summarize anti-tetanus and anti-diphtheria antibody titers. All data will be presented in listings.

Analyses will be done using SAS v9.4.

9.2. Participant Accountability and Protocol Deviations

The disposition of all study subjects will be summarized including the total numbers screened, eligible, enrolled, ITT, per-protocol, withdrawn, and completed. Accountability data including study termination and reason will be provided in a summary table and listing for all subjects who were enrolled. A listing of all protocol deviations will be provided.

9.3. Demographics, Pre-donation Screening and Treatment Compliance

Subject demographics which includes age (years), gender, ethnicity and race will be summarized for the ITT and Per-protocol population. Pre-donation screening for plasmapheresis check includes full physical examinations, vital signs, total proteins and hematocrit at each donation, will be summarized by visit and listed by subject and visit. Compliance with scheduled vaccinations will also be summarized, including number of doses and total dose of investigational product. Protocol compliance will be presented as percentages of subjects attending scheduled visits over the duration of the study.

9.4. Immunizations, Prior and Concomitant Medications

Prior and concomitant medications will be listed by subject. Medications and treatments with an end date prior to the first dose of study drug will be considered prior medications and will be noted in listing. If the date is partial or unknown, then medication will be considered as concomitant. Any prior immunizations will be listed by subject.

9.5. Analysis of Safety Endpoints

Treatment emergence will be evaluated for all AEs. Treatment-emergent adverse events (TEAEs) are those that occur on or after the same date and time of first dose of study drug. TEAEs will be coded using the most recent version of the Medical Dictionary of Regulatory Affairs (MedDRA) by assigning a preferred term and will be grouped by system, organ, and class (SOC) designation. AEs occurring after each vaccination up to the time of the next vaccination and separately over the whole study period will be summarized. Separate tables will be provided for solicited AEs reported within the 3 day period after each vaccination.

Each AE will be counted once only by preferred term for a given study subject within each post vaccination time period prior to the next vaccination or up to the 6-month follow-up visit after the last vaccination. If the same AE occurred on multiple occasions, the highest severity and relationship to investigational product will be assumed within each time period.

The summary tables will include an overall summary of number and percentage of subjects reporting each TEAE, summary by relationship, summary by severity will be presented by each vaccination period and overall.

Listings of each individual AE including start date, stop date, severity, relationship, duration, outcome, and actions taken will be provided.

Reactogenicity is defined as the total count of a set of solicited AEs that are expected after a vaccine. A regression analysis will be performed with reactogenicity as the dependent variable and anti-diphtheria titers as the independent variable to determine if there is an association. Anti-diphtheria titer is not expected to be normally distributed and will be natural log transformed. Null Hypothesis of no association between reactogenicity and anti-diphtheria titers will be tested on

Slope obtained using simple linear regression analysis at alpha=0.01 using two-sided tests. The null hypothesis states that the slope is equal to zero, and the alternative hypothesis states that the slope is not equal to zero. No adjustment for covariates will be made. The following SAS procedure PROC REG may be used.

```
Proc reg data=data;
Model reactogenicity =log(anti_diphtheria_titers);
Run;
```

In addition, 2x2 tables will be created with presence or absence of moderate to severe reactogenicity versus high or not anti-diphtheria titers. Cut points of 75th percentile or 90th percentile of the anti-diphtheria titers will be used to define high level. The following SAS procedure PROC FREQ may be used.

```
Proc freq data=data;
Table reactogenicity*anti_diphtheria_titers/nopercent nocol;
Weight count;
Run;
```

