11.2.8.2. Documentation of Adverse Events

At each visit, the study staff will assess the occurrence of AEs by asking the subject a non-leading question such as “Do you feel different in any way since your last visit?” Additionally, the study staff will ask study participants about any medically attended AEs, hospitalizations, and newly diagnosed chronic medical conditions.

In addition, subjects will be given a diary at the screening visit. The investigator will explain that the diary is a very important study document and that entries should be made daily in order to collect all safety data. The diary is set up for the subject to record new AEs that occur during each month of the study. The diary will also contain daily solicitation of expected AEs including injection site redness, tenderness, induration or pain, urticaria or other rash, fatigue, malaise, headache, fever, chills, nausea, joint pain, and muscle weakness including a severity rating scale. Solicited AEs to be recorded in the diary will be those that occur for up to 3 days after each vaccination. The diary will be reviewed at each visit. The subject will enter the following information in the diary:

- All new AEs that occurred each month of the study.
- Solicited AEs and severity that occurred up to 3 days after each vaccination.
- Any medication taken, prescription and non-prescription used to treat an AE.

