3.2. Study Design

This is a prospective, open label, single-arm, multi-center, Phase 2 study measuring the safety and tetanus antibody responses to Tdap vaccine administered to plasma donors every 3 months ± 1 week for 12 months (5 vaccinations) with a 6 month follow-up after the last vaccination. After obtaining informed consent and screening for eligibility including plasmapheresis donor eligibility, subjects will have other baseline assessments performed and if eligible, will receive the scheduled vaccinations, will be assessed for adverse events (AEs) and have plasma samples collected with antibody titers reported each month thereafter for 11 months, and then at 1 and 6 months after the last vaccination. Subjects will undergo plasmapheresis prior to the second through the fifth vaccination and at the 1 month and 6 month post vaccination follow-up visits. As these subjects are participating in a standard donor plasmapheresis donor program, assessments for donor eligibility and routine plasmapheresis will be performed; however, only the data specifically required to meet the objectives of this study will be collected.

The study time and events schedule is shown in [Table A](#). In addition to these study specific assessments routine screening procedures to assure plasma donor suitability was also performed. Some of the routine procedures performed as part of plasma donor screening evaluations such as vital signs, physical examinations, or laboratory tests were reported as AEs (if appropriate) on an AE eCRF.

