3.3. Study Endpoints

Safety Endpoints:

- Incidence, severity, and relationship of AEs to the study vaccine in the time period between vaccinations and for the overall study period.

Efficacy endpoints:

- Anti-tetanus antibody titer levels after each vaccination presented at geometric means (GeoMean) over time.
- The numbers and percentages of subjects whose post vaccination antibody levels are <5 IU/mL; ≥ 5 IU/mL to 10 IU/mL; >10 IU/mL to 15 IU/mL; and >15 IU/mL after each vaccination.

Table A: Time and Events Schedule

Study Phase	Screening	Visits (Month 0 to Month 12 ± 1 week)												
Month	-7 to -1 days	0	1	2	3	4	5	6	7	8	9	10	11	12
Visit Number	1	2/3	4	5	6/7	8	9	10/11	12	13	14/15	16	17	18/19
Study Specific Procedures for which data are recorded on an eCRF														
Consent	X													
Eligibility checklist ^a	X	X			X			X			X			X
Demographics	X													
Medical history	X													
Medications	X	X			X			X			X			X
Vaccination		1			2			3			4			5
AEs	X	X	X	X	X	X	X	X	X	X	X	X	X	
Plasma sample for anti-tetanus and anti-diphtheria antibody titer ^b	X		X	X	X	X	X	X	X	X	X	X	X	
Urinalysis/ serum creatinine ^c		X			X			X			X			X
Diary card review ^d		X	X	X	X	X	X	X	X	X	X	X	X	
Procedures performed as part of routine plasma donor testing and pheresis														
Medical history ^e	X	X	X	X	X	X	X	X	X	X	X	X	X	
Body weight	X	X	X	X	X	X	X	X	X	X	X	X	X	
Infectious diseases ^f	X													
Immunization record	X													
Medications	X	X	X	X	X	X	X	X	X	X	X	X	X	
Pre-donation screening examination ^g	X	X	X	X	X	X	X	X	X	X	X	X	X	
Plasmapheresis			Plasma donations may occur 2-times per week with at least one-calendar day between donations.											

^aAt screening, the reasons a subject is not eligible for the study (screen failure) will be captured on a Reasons Not Eligible eCRF. Subjects will be checked to ensure that they meet study eligibility criteria prior to each vaccination. If not eligible, a Reasons not Eligible for Vaccination eCRF will be completed.

^bTetanus and diphtheria antibody test samples will be collected, frozen and tested at a later date. Samples are collected from plasma donations performed at these visits. If a plasmapheresis was not scheduled or performed at this visit (\pm 1 week) then a blood sample collected for plasma separation may be used instead.

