Note: AEs occurring after each vaccination up to the time of the next vaccination is summarized.

<Program Name: Time and Date>

Table 7: Summary of Solicited Treatment-emergent Adverse Events - ITT Population

	Vaccination Number					Overall N=xx
	1 N=xx	2 N=xx	3 N=xx	4 N=xx	5 N=xx	
Number of Solicited TEAEs	xx	xx	xx	xx	xx	xx
Number of AEs related to study product	xx	xx	xx	xx	xx	xx
Number (%) of subjects with						
At least one solicited TEAE	xx (x.x%)	xx (x.x%)	xx (x.x%)	xx (x.x%)	xx (x.x%)	xx (x.x%)
At least one AE related to study product	xx (x.x%)	xx (x.x%)	xx (x.x%)	xx (x.x%)	xx (x.x%)	xx (x.x%)
Number of Solicited TEAEs by severity						
Mild	xx	xx	xx	xx	xx	xx
Moderate	xx	xx	xx	xx	xx	xx
Severe	xx	xx	xx	xx	xx	xx
Number of Solicited TEAEs by						
relationship to study product	xx	xx	xx	xx	xx	xx
Unrelated	xx	xx	xx	xx	xx	xx
Unlikely	xx	xx	xx	xx	xx	xx
Possible	xx	xx	xx	xx	xx	xx
Probable	xx	xx	xx	xx	xx	xx
Definite						

N = Number of Subjects

Note: Solicited AEs reported within the 3 day period after each vaccination is summarized.

<Program Name: Time and Date>

Table 8: Number (%) of Subjects with Treatment-emergent Adverse Events by System Organ Class and Preferred Term - ITT Population

System, Organ, Class/ Preferred Term	Vaccination Number					Overall N=xx n (%)
	1 N=xx n (%)	2 N=xx n (%)	3 N=xx n (%)	4 N=xx n (%)	5 N=xx n (%)	
SOC 1	xx (xx.x)					
Preferred Term 1	xx (xx.x)					
SOC 2	xx (xx.x)					
Preferred Term 2	xx (xx.x)					

Note: Subjects are counted only once within each system organ class and preferred term.

<Program Name: Time and Date>

Table 9: Number (%) of Subjects withSolicited Treatment-emergent Adverse Events by System Organ Class and Preferred Term - ITT Population

System, Organ, Class/ Preferred Term	Vaccination Number					Overall N=xx n (%)
	1 N=xx n (%)	2 N=xx n (%)	3 N=xx n (%)	4 N=xx n (%)	5 N=xx n (%)	
SOC 1	xx (xx.x)					
Preferred Term 1	xx (xx.x)					
SOC 2	xx (xx.x)					
Preferred Term 2	xx (xx.x)					

: Note: Solicited AEs reported within the 3 day period after each vaccination is summarized.

Subjects are counted only once within each system organ class and preferred term.

<Program Name: Time and Date>

Table 10: Summary of Subjects with Treatment-emergent Adverse Events by Severity and Relationship - ITT Population

System, Organ, Class\ Preferred Term	Number of Subjects (%) (N=xx)								
	Mild		Moderate		Severe		All Grades		Total
	R	NR	R	NR	R	NR	R	NR	R + NR
SOC									

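### The all-AE tables pool about 91 days after doses 1-4 and about 183 days after dose 5, with no split by time since dose and no person-time rates

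*SAP*

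**What the plan says.** SAP section 3.2 describes the design: "This is a prospective, open label, single-arm, multi-center, Phase 2 study". Safety is the primary objective, and the safety endpoint in SAP section 3.3 is "Incidence, severity, and relationship of AEs to the study vaccine in the time period between vaccinations and for the overall study period".

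For AEs in general, SAP section 9.5 sets one period per dose: "AEs occurring after each vaccination up to the time of the next vaccination and separately over the whole study period will be summarized". Each preferred term is counted once per subject "within each post vaccination time period prior to the next vaccination or up to the 6-month follow-up visit after the last vaccination", at the highest severity and closest relationship. The note under Table 6 in SAP Appendix A repeats the period: "Note: AEs occurring after each vaccination up to the time of the next vaccination is summarized". Tables 6 and 8 have columns for vaccinations 1 to 5 and overall. The Table 10 shell (severity by relationship) has no vaccination columns.

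The only shorter window is in Tables 7 and 9, for solicited AEs within 3 days of a dose. Under protocol section 11.2.8.2 those items are solicited for up to 3 days only.

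The data for a finer split exist. Other AEs are recorded throughout the study in a diary in which "entries should be made daily in order to collect all safety data". Listing 8 gives each vaccination date. Listing 11 gives onset date, onset day and vaccine number, although its shell does not say from which dose onset day is counted.

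**The concern.** With no control arm, a column total has nothing to be read against. An AE on day 2 and one on day 85 after the same dose count alike, so a short post-dose excess is mixed with weeks of background events. Timing enters the summary tables only through the relationship rating, which an unblinded investigator assigns partly on timing. Comparing event rates soon after a dose with rates later in the same subject's interval would not depend on that rating, but the SAP does not plan it.

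The unequal column lengths are a second problem. Tables 6 and 8 invite a comparison of later doses with the first, which bears on the question of repeated dosing. Counts and percentages from a column twice as long are not comparable with the others, and without person-time the reader cannot correct for it.

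**Working it through.** **Inputs from the documents.** The schedule is "every 3 months ± 1 week for 12 months (5 vaccinations) with a 6 month follow-up after the last vaccination" (SAP section 3.2). SAP section 7 gives 100 subjects, with no effect size, AE rate or power, so there is no planned figure to reproduce.

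**Assumptions, none given in the documents.** Background AE rate, true rate ratio (RR), length of the raised-risk window, constant background, independent events, no dropout.

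**1. Column lengths.**
- Columns 1-4: 3 × 365.25/12 = 91.3 days.
- Column 5: 6 × 365.25/12 = 182.6 days.
- Person-time for 100 subjects: 100 × (4 × 91.3 + 182.6)/365.25 = 150 person-years, of which column 5 holds 182.6/547.9 = one third.

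**2. Dilution of an early excess.** If the rate is multiplied by RR in days 0-14 (15 days) of a column of L days, the expected total rises by (RR − 1) × 15/L. For RR = 2:
- Doses 1-4: 15/91.3 = 16.4%.
- Dose 5: 15/182.6 = 8.2%.

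**3. Column 5 with no vaccine effect.** Expected event counts are in the ratio 182.6/91.3 = 2.0 (slightly less once repeats of a term are collapsed). At an assumed 1 AE per person-year, the share of subjects with at least one AE is 1 − exp(−0.25) = 22% in each of columns 1-4 and 1 − exp(−0.5) = 39% in column 5.

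**4. What a within-subject contrast could show.** Cap every dose at day 90, giving 91 days (0-90), with days 15-90 (76 days) as comparison. With 100 × 5 = 500 intervals and λ background events per interval, expected events are 500 × λ × W/91 × RR in a risk window of W days and 500 × λ × 76/91 in the comparison window. SE(ln RR) = √(1/risk + 1/comparison). For true RR = 2:

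| λ per interval | Days 0-14 (W = 15): events, 95% CI | Days 4-14 (W = 11): events, 95% CI |
|---|---|---|
| 0.1 | 16.5 v 41.8, 1.13-3.54 | 12.1 v 41.8, 1.05-3.79 |
| 0.3 | 49.5 v 125.3, 1.44-2.78 | 36.3 v 125.3, 1.38-2.89 |
| 1.0 | 164.8 v 417.6, 1.67-2.40 | 120.9 v 417.6, 1.63-2.45 |

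On a yearly scale, λ = 0.1 is 0.1 × 365.25/91 = 0.40 events per person-year. For rarer events the contrast is weak. An exact conditional calculation (14-day window against all remaining follow-up, two-sided 0.05, RR = 2) gives 14% power at 0.1, 36% at 0.25, 64% at 0.5 and 91% at 1 event per person-year.

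**5. A trap in the construction.** Solicited terms such as headache or fatigue must not be dropped from days 0-3 alone while all 15 days stay in the denominator. For those terms a true RR of 1 would then read 11/15 = 0.73, and a true RR of 2 would read 2 × 11/15 = 1.47.

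**The case against.** The strongest reply is that the SAP does what the protocol asks. The endpoint is defined by the period between vaccinations, so this is a request for an added analysis and not the correction of an error. That stands, and it limits the weight of the point.

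A reader might infer that the trial discards its only internal control and leaves causality wholly to unblinded opinion. The documents do not support that:
- Nothing is discarded. Listings 8 and 11 keep vaccination dates, onset dates and vaccine number, and SAP section 2 permits post hoc exploratory analyses. What is missing is tabulation and prespecification. A window chosen after seeing open-label data is open to selection.
- Tables 6 to 9 also set dose 1 beside doses 2-5. That is another internal comparison, though confounded with calendar time and dropout and, in Tables 6 and 8, with the longer fifth period.
- The relationship criteria use temporal sequence, the medical monitor advises on SAE relatedness and follows AE trends (protocol section 10), and the renal laboratory results have numerical thresholds (SAP section 9.6).

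It is also fair to say that an early-versus-late contrast addresses the acute effect of a dose. A cumulative effect of repeated dosing, such as the glomerular disease that the protocol monitors for, could raise both windows and cancel out. Finally, the day 0-14 window comes from the protocol's reference rates for injection-site and solicited systemic reactions (section 4.5), so its relevance to other AEs is a judgement.

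**Conclusion.** The point holds as a gap in tabulation and prespecification. Tables 6 and 8 pool periods of about 91 days (doses 1-4) and 183 days (dose 5) without a split by time since dose or person-time rates, Table 10 pools the whole study, and the 3-day solicited tables have no comparison window. A doubling confined to days 0-14 would move a column total by about 16% or 8%. Column 5 would show about twice the events of the others under a constant background with no vaccine effect.

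The period lengths follow from the schedule. The dilution figures rest on the assumed RR and window, and the precision figures also on the assumed background rate and full follow-up. The change is a cheap improvement worth making. The finding does not invalidate the planned tables.

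**What to change.** Before database lock, add to SAP section 9.5 one table of AE onsets by days since last dose, by dose and overall:
- Windows 0-3, 4-14, 15-30, and 31 to the day before the next dose, capped at day 90 for every dose including dose 5.
- Events per person-day, from each subject's actual days at risk, for all AEs and for moderate or severe AEs.
- Each new onset counted, in place of once per preferred term per period.
- Solicited diary items shown separately from other AEs.
- Onsets with a missing day excluded, because SAP section 10 sets them to the first of the month and can move them to another window or before the dose. Add a sensitivity analysis that includes them.

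If a within-subject rate ratio with 95% CI is reported, label it exploratory. Use either days 4-14 against days 15-90 for all AEs, or days 0-14 against days 15-90 only for terms never solicited in the diary.

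The cost is SAP text and one table from data already collected. State the limits with the result: closer questioning soon after each dose (the vaccination-day query and the visit 1 to 3 days later) can favour the early window, the contrast is imprecise for rare events, and it does not capture late or cumulative effects of repeated dosing.

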4.3. Benefit/Risk Statement

Vaccination of plasma donors is expected to produce elevated tetanus antibody levels in all recipients. The presence of circulating tetanus antibodies has been shown to protect against accidental infection with *C. tetani*. Participants in this study should obtain levels of tetanus antibody that will protect them against any subsequent infection by *C. tetani*.

Pain at the injection site is expected to be the most common AE lasting for 0-14 days after vaccination. In clinical trials, 65.7 % of recipients experienced injection site pain (prescribing information; [Sanofi Pasteur-2017](#)). Injection site swelling, erythema and fever occurred at rates of 21.0%, 24.7% and 1.4%, respectively ([Sanofi Pasteur-2017](#)).

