Characteristic	ITT N=xx	Per-protocol N=xx
Gender		
Male	xx (x.x%)	xx (x.x%)
Female	xx (x.x%)	xx (x.x%)
Age (years at date of consent)		
Mean (SD)	xx.x (x.xx)	xx.x (x.xx)
Median	xx.x	xx.x
Min-Max	(xx – xx)	(xx – xx)
Maximum		
Race		
Black or African American	xx (x.x%)	xx (x.x%)
American Indian or Alaskan Native	xx (x.x%)	xx (x.x%)
Asian	xx (x.x%)	xx (x.x%)
Native Hawaiian or Other Pacific Islander	xx (x.x%)	xx (x.x%)
White	xx (x.x%)	xx (x.x%)
Other/Unknown	xx (x.x%)	xx (x.x%)
	xx (x.x%)	xx (x.x%)
Ethnicity		
Hispanic or Latino	xx (x.x%)	xx (x.x%)
Not Hispanic or Latino	xx (x.x%)	xx (x.x%)
Not Reported	xx (x.x%)	xx (x.x%)

<Program Name: Time and Date>

Table 4: Summary of Protocol and Treatment Compliance

	ITT N=xx
Protocol compliance rate^a	
Month 0	xx.x%
Month 3	xx.x%
Month 6	xx.x%
Month 9	xx.x%
Month 12	xx.x%
Number of Tdap vaccinations	
Mean (SD)	xx.x (x.xx)
Median	xx.x
Min-Max	(xx – xx)
Total Tdap vaccination dose (mL)	
Mean (SD)	xx.x (x.xx)
Median	xx.x
Min-Max	(xx – xx)

^aProtocol compliance is presented as percentages of subjects attending each scheduled treatment visit.

<Program Name: Time and Date>

Table 5: Summary of Plasmapheresis Check by Visit - ITT Population

Visit		n (%)
Screening	Eligible for Plasmapheresis	
	Yes	xx.x (x.xx)
	No, Temporary	xx.x (x.xx)
	No, Permanent	xx.x (x.xx)
	If "No, Temporary", Inclusion Criteria not Met	
	Temperature: 97.0 - 99.5 °F	xx.x (x.xx)
	Blood Pressure: 90 - 180/50 - 90 mmHg	xx.x (x.xx)
	Pulse: 50 - 100 beats/min	xx.x (x.xx)
	(List all criteria not met)	
(Repeat for all visits)		

<Program Name: Time and Date>

Table 6: Summary of Treatment-emergent Adverse Events - ITT Population

	Vaccination Number					Overall N=xx
	1 N=xx	2 N=xx	3 N=xx	4 N=xx	5 N=xx	
Number of AEs	xx	xx	xx	xx	xx	xx
Number of SAEs	xx	xx	xx	xx	xx	xx
Number of AEs related to study product	xx	xx	xx	xx	xx	xx
Number (%) of subjects with						
At least one AE	xx (x.x%)	xx (x.x%)	xx (x.x%)	xx (x.x%)	xx (x.x%)	xx (x.x%)
At least one SAE	xx (x.x%)	xx (x.x%)	xx (x.x%)	xx (x.x%)	xx (x.x%)	xx (x.x%)
At least one AE related to study product	xx (x.x%)	xx (x.x%)	xx (x.x%)	xx (x.x%)	xx (x.x%)	xx (x.x%)
Number of AEs by severity						
Mild	xx	xx	xx	xx	xx	xx
Moderate	xx	xx	xx	xx	xx	xx
Severe	xx	xx	xx	xx	xx	xx
Number of AEs by relationship to study product						
Unrelated	xx	xx	xx	xx	xx	xx
Unlikely	xx	xx	xx	xx	xx	xx
Possible	xx	xx	xx	xx	xx	xx
Probable	xx	xx	xx	xx	xx	xx
Definite						
Serious?						
Yes	xx	xx	xx	xx	xx	xx
No						

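### SAP Tables 6, 8 and 10 pool expected 3-day reactions with all other AEs, and no unsolicited-only summary of subjects is planned

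*SAP*

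**What the plan says.** Safety of the repeated schedule is the primary objective (Protocol 5, SAP 3.1). The endpoint is AE incidence, severity and relationship, per vaccination interval and overall (SAP 3.3). The only hypothesis test is the slope of reactogenicity on anti-diphtheria titer, by "simple linear regression analysis at alpha=0.01 using two-sided tests" (SAP 6). The sample size is stated without derivation: "One hundred subjects will be enrolled in this study" (SAP 7). The descriptive AE tables are therefore the main AE analysis.

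SAP 9.5 defines the events that enter these tables by timing alone: "Treatment-emergent adverse events (TEAEs) are those that occur on or after the same date and time of first dose of study drug". Solicited reactions are not taken out. The note to Table 6 in SAP Appendix A gives the window: "AEs occurring after each vaccination up to the time of the next vaccination is summarized". That is about three months, or about six after dose 5. Table 6 has a row for subjects with "At least one AE", for each vaccination and overall. Table 8 is titled "Number (%) of Subjects with Treatment-emergent Adverse Events by System Organ Class and Preferred Term - ITT Population" and has SOC and preferred-term rows only.

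For solicited reactions, SAP 9.5 adds: "Separate tables will be provided for solicited AEs reported within the 3 day period after each vaccination". These are Tables 7 and 9. None of the 15 table shells is restricted to unsolicited AEs, although the diary collects both kinds (Protocol 11.2.8.2).

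SAP 9.5 also counts each preferred term once per subject per vaccination period, at the highest severity and closest relationship.

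**The concern.** Protocol 5 asks whether dosing more often than the licensed schedule is safe. The short-term reactions to a single dose are already described by the label; the Protocol notes that "65.7 % of recipients experienced injection site pain" (Protocol 4.3). New or later events under repeated dosing have no such background figure, and the vaccination columns of Table 6 are where a rise across doses would be looked for. If most subjects already count in the any-AE row because of a sore arm or a headache, a rise in other AEs among those subjects leaves the row unchanged. The counting rule adds a second, narrower problem: for a term that the diary solicits, an expected reaction soon after a dose and a separate episode weeks later become one record.

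**Working it through.** The plan gives no expected any-AE rate, no unsolicited rate and no power statement, so there is no figure of its own to reproduce.

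**Inputs**
- s, the chance of at least one solicited reaction after a dose: not given for this study. The only background is the label rates for days 0-14 in Protocol 4.5, Tables 2 and 3.
- u, the chance of at least one unsolicited AE in a vaccination period: given nowhere, so assumed here at 5% to 40%.
- N = 100 (SAP 7).

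**Step 1: formula.** If the two kinds of event are independent, P(any AE) = 1 − (1 − s)(1 − u). A change Δu moves the merged row by (1 − s)Δu and an unsolicited-only row by Δu.

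**Step 2: range for s.** The any-reaction rate cannot be below its largest component, so if the label pain rate applies, s ≥ 65.7%. Eleven label items match diary items: pain 65.7%, swelling 21.0%, erythema 24.7%, fever 1.4%, headache 33.9%, body ache or muscle weakness 21.9%, fatigue 24.3%, chills 8.1%, joints 9.1%, nausea 9.2%, rash 2.0%. If these were independent, s = 1 − (0.343 × 0.790 × 0.753 × 0.986 × 0.661 × 0.781 × 0.757 × 0.919 × 0.909 × 0.908 × 0.980) = 94.2%. With a common latent-normal correlation of 0.3, 0.5 or 0.7, s is 83.5%, 76.7% or 70.4%. A value of 50% is added in case the 3-day window lowers s.

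**Step 3: the merged row when u doubles**

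| s | Share of change shown | u 5→10% | u 10→20% | u 20→40% |
|---|---|---|---|---|
| 50% (assumed) | 50% | 52.5→55.0% | 55.0→60.0% | 60.0→70.0% |
| 65.7% | 34% | 67.4→69.1% | 69.1→72.6% | 72.6→79.4% |
| 80% | 20% | 81.0→82.0% | 82.0→84.0% | 84.0→88.0% |
| 94.2% | 6% | 94.4→94.7% | 94.7→95.3% | 95.3→96.5% |
| Unsolicited-only row | 100% | 5→10% | 10→20% | 20→40% |

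For scale, the standard error of 69.1% at N = 100 is √(0.691 × 0.309 / 100) = 4.6 points, against a move of 3.4 points at s = 65.7% and u 10→20%. The 95% half-width at 84% is 1.96 × √(0.84 × 0.16 / 100) = 7.2 points, against a move of 4.

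**Step 4: can the missing figure be recovered?** Table 6 minus Table 7 approximates unsolicited event counts. It does not give subjects. If 79.4% have any AE and 65.7% a solicited one, those two rows alone allow an unsolicited percentage anywhere from 79.4 − 65.7 = 13.7% to 79.4%. The value that generated them was 40%.

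**Step 5: the once-only rule.** Take a mild, related headache on Day 1 and a severe, unrelated headache at week 8 of the same period. In Table 8 the subject counts once for headache. In Table 10 the subject can appear as one severe, related headache, a combination that matches neither event. The Table 10 shell has no vaccination columns, so as drawn the merging spans the whole study. Subtraction in Step 4 also loses the week 8 episode. A preferred term that is not on the diary list has its own row and is untouched by any of this.

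**The case against.** A reader might infer that the any-AE row sits near its ceiling at every dose, so that even a doubling of unexpected AEs would barely move it. The documents do not support that. The 94% figure needs eleven reactions to be independent; the correlations tried give about 70% to 84%. The label rates cover 14 days against 3 here, the diary grades redness and swelling only from 2.5 cm (Protocol Table 5), and no rates are given for doses 2 to 5. The size of the movement also depends on an unsolicited rate that is an assumption: at s = 65.7%, a doubling from 40% to 80% would move the row from 79.4% to 93.1%, or 13.7 points.

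A reader might also extend the dilution to Table 8. That fails: Table 8 has no any-AE row, and a new preferred term outside the diary list appears there undiluted, by vaccination.

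Other points for the plan are fair. Increased reactogenicity is itself a stated concern with its own analysis (SAP 9.5), and glomerular disease is monitored through laboratory data (SAP 9.6). The SAE rows are not masked. Listing 11 shows every AE with its onset day, so a later episode is merged in the counts but not lost from the report. The standard errors above describe a single percentage, not a within-subject comparison between doses, and no test of AE incidence is planned.

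These points narrow the concern to Table 6 and to the shared terms. They do not supply the missing summary: listings are not a tabulation, and Step 4 shows that subject counts cannot be obtained by subtraction.

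**Conclusion.** The gap is real but limited. No planned table gives the number of subjects with an unsolicited AE, by dose or overall. If s is at least 65.7% and independent of unsolicited AEs, Table 6's any-AE row shows at most about one third of a change in unsolicited incidence; at s = 80% it shows one fifth. If the shorter window brought s down to 50%, half would show. A positive association between the two kinds of event, such as subjects who report everything, would leave less visible than the formula says. The point movements rest on assumed unsolicited rates.

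In Tables 8 and 10 the problem is confined to terms shared with the diary, such as headache, fatigue, nausea and joint pain, and to their SOC rows. This does not invalidate the safety analysis. It is an inexpensive improvement that is worth making because safety under repeated dosing is the primary question.

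**What to change.** Add unsolicited-only versions of Table 6 (with a row for subjects with at least one unsolicited AE) and Table 8, by vaccination number and overall. Define the set as all treatment-emergent AEs except solicited terms with onset within 3 days of a dose. This puts a solicited term that starts after day 3 in the unsolicited set; say so, and state how a reaction that starts within 3 days and persists beyond them is classified. Apply the once-only, highest-severity-and-relationship rule separately to the solicited and unsolicited sets, so that an early reaction does not absorb a later episode of the same term. An unsolicited-only Table 10 is optional.

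The cost is two extra tables, produced by rerunning existing programs with the flag that Listing 12 already needs. No new data are collected.
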